4 ANALYSIS SETS, TREATMENT GROUPS, AND SUBGROUPS

4.1 Analysis Sets

The following populations will be evaluated and used for presentation and analysis of the data:

- Enrolled subjects: Subjects who signed an informed consent form and were assigned a Patient Identification number (PID).
- Randomized subjects: Enrolled subjects who received a treatment assignment from the IWRS.
- Treated/Safety: Enrolled subjects who received at least 1 dose of blinded study therapy (Verdiperstat or placebo).
- Modified Intent-to-Treat (mITT) subjects: Randomized subjects who received at least one dose of blinded study therapy and provided a baseline and at least one post-baseline efficacy assessment.
- Open-Label Extension Treated subjects: Enrolled subjects in the extension phase who received at least 1 dose of open-label study therapy (Verdiperstat).
- Verdiperstat Treated Participants: Enrolled subjects who received at least 1 dose of Verdiperstat (blinded or open-label)

4.2 Treatment Groups

The 2 treatment groups are Verdiperstat and placebo.

Populations of treated subjects will be assessed by the as-treated treatment group, i.e., by the treatment actually received. Otherwise, all other populations will be assessed by the asrandomized treatment group. The enrolled population will be assessed overall.

4.3 Subgroups

The following subgroups are of interest:

- Sex (male, female)
- Race (Asian, Black or African American, White, and Other)
- Age ($<65, \ge 65 \text{ years}$)
- Smoking status (current, previous, never)
- Disease subtype (MSA-P, MSA-C)
- MSA diagnostic category (Possible, Probable)
- Country
- Concomitant background therapy use for Parkinson's Disease (yes, no)

5 SAMPLE SIZE, POWER, AND TYPE I ERROR

5.1 Sample Size and Power

The sample size for this study will be approximately 325 randomized subjects.

Based on unpublished data from the Promesa (2016) study.² studying EGCG (epigallocatechingallate) vs placebo with a treatment duration of 48 weeks, the placebo group had a 4.88 point increase with a standard deviation of 4.85 in the modified UMSARS Part I and Part II total score. With an expected improvement of 40% at Week 48 for Verdiperstat compared to placebo, a total of 260 subjects (130 per group) provides 90% power based on a 2-sample, two-sided t-test. With a drop-out rate of ~20%, the study will randomize approximately 325 subjects.

5.2 Type I Error

Type-1 error will be controlled for the primary and key secondary efficacy endpoints by testing them with a gate-keeping procedure. The primary endpoint, the change from baseline in the modified UMSARS score measured at the Week 48 visit, will be tested at a 2-sided alpha level of 0.05. If this test is significant, then the key secondary efficacy endpoints of change from baseline in CGI-I, MSA-QoL motor subscale and non-motor subscale scores, and UMSARS Part I and Part II total score at week 48 will be tested using Hochberg's procedure in which the p-values from the test of each secondary endpoint will be ranked from lowest to highest, and all tests for the null hypothesis of each secondary endpoint with a p-value less than the test with the highest p-value below its critical p-value (defined as 0.05/(k-j+1) where j is the rank of the test and k is the total number of tests) can be rejected.

If the test of the primary endpoint is not significant, then the unadjusted p-values for the key secondary endpoints will be presented only for descriptive purposes, and no conclusions will be drawn from these results.

No attempt will be made to adjust for multiplicity when testing the non-key secondary or endpoints. Any endpoints subjected to significance testing are evaluated at an unadjusted two-sided alpha level of 0.05.

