9.4.5 Adjustment for Multiplicity

Type-1 error will be controlled for the primary and key secondary efficacy endpoints by testing them with a gate-keeping procedure. The primary endpoint will be tested at a two-sided alpha level of 0.05. If this test is significant, then the key secondary efficacy endpoints will be tested using Hochberg's procedure. If the test of the primary endpoint is not significant, then the unadjusted p-values for the key secondary endpoints will be presented only for descriptive purposes.

No attempt will be made to adjust for multiplicity when testing the non-key secondary or CCI endpoints. Any endpoints subjected to significance testing are evaluated at an unadjusted two-sided alpha level of 0.05.

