6.3.3 Secondary Efficacy Endpoints

If the main analysis of the primary endpoint is significant, then the main analyses of the key secondary endpoints are tested using the Hochberg procedure, as described in Section 5.2. The key secondary endpoints include: CGI-I; MSA-QoL motor subscale; MSA-QoL non-motor subscale; UMSARS Part I and Part II Total Score.

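### SAP 5.2 names Hochberg's procedure, but its decision sentence read literally leaves out the qualifying endpoint; the wording should be aligned with the named method

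*SAP*

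**What the plan says.** SAP 5.2 (Type I Error) sets a gate. The primary endpoint "will be tested at a 2-sided alpha level of 0.05", and only if it succeeds are the key secondaries tested. SAP 6.3.3 lists them: "The key secondary endpoints include: CGI-I; MSA-QoL motor subscale; MSA-QoL non-motor subscale; UMSARS Part I and Part II Total Score".

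For this family SAP 5.2 names Hochberg's procedure and describes it in three parts:

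- Ordering: "the p-values from the test of each secondary endpoint will be ranked from lowest to highest".
- Critical p-value: "defined as 0.05/(k-j+1) where j is the rank of the test and k is the total number of tests".
- Decision: the null hypothesis can be rejected for tests "with a p-value less than the test with the highest p-value below its critical p-value".

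SAP 6.3.3 adds that "the main analyses of the key secondary endpoints are tested using the Hochberg procedure, as described in Section 5.2", which sends the reader back to that description. Protocol 9.4.5 says that after a significant primary result "then the key secondary efficacy endpoints will be tested using" Hochberg's procedure, and gives no steps. No other section of either document restates or corrects the decision rule.

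**The concern.** Hochberg's step-up procedure finds the largest rank at which the ordered p-value meets its critical value. It then rejects that hypothesis together with all hypotheses of lower rank. The SAP's decision clause uses a strict inequality against the qualifying p-value, and no other clause rejects the qualifying test itself. SAP 5.2 therefore names one procedure and, taken word for word, describes a smaller rejection set.

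This is the confirmatory decision rule for all four key secondary endpoints, and it will be applied once the p-values are known. The endpoint in question is always the qualifying one, that is, the weakest of the results that would be claimed. Following the wording gives up a claim that Hochberg's procedure supports. Following the name makes a claim that the written steps do not include, and that choice would be made with the data in view.

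**Working it through.** **Inputs.** Family level 0.05 and the critical-value formula (SAP 5.2); p-values ranked in ascending order (SAP 5.2); k = 4 (SAP 6.3.3).

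**Step 1: critical values.** 0.05/(4−j+1) for j = 1 to 4:

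- j = 1: 0.05/4 = 0.0125
- j = 2: 0.05/3 = 0.0167
- j = 3: 0.05/2 = 0.025
- j = 4: 0.05/1 = 0.05

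These are the standard Hochberg constants, so this part of SAP 5.2 is right.

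**Step 2: the two rejection sets.** Let j* be the largest rank with p(j) below its critical value.

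- Hochberg: reject every hypothesis with p ≤ p(j*).
- SAP 5.2 read literally: reject every hypothesis with p < p(j*).

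The second set never contains the hypothesis at j*. The largest of the four p-values can never be below p(j*), so at most three rejections are possible. If j* = 1 there are none.

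**Step 3: examples.**

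| Ordered p-values | j* | Literal rule | Hochberg |
|---|---|---|---|
| 0.001, 0.2, 0.3, 0.4 | 1 | 0 | 1 |
| 0.001, 0.01, 0.03, 0.2 | 2 | 1 | 2 |
| 0.001, 0.002, 0.024, 0.2 | 3 | 2 | 3 |
| 0.01, 0.02, 0.03, 0.04 | 4 | 3 | 4 |
| 0.04, 0.04, 0.04, 0.04 | 4 | 0 | 4 |

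Without ties the difference is exactly one rejection whenever some endpoint qualifies. With ties it can be more. When nothing qualifies there is no difference.

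**Step 4: type I error.** The literal set is always contained in the Hochberg set, so it cannot inflate error. A simulation with all four nulls true (200,000 runs, equicorrelated normal statistics) gave these familywise error rates:

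| Correlation | Literal | Hochberg |
|---|---|---|
| 0 | 0.002 | 0.049 |
| 0.3 | 0.005 | 0.047 |
| 0.5 | 0.009 | 0.043 |
| 0.7 | 0.015 | 0.038 |

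**Step 5: illustration of the loss.** The documents give no effect size, power or correlation for the key secondaries, so the values here are assumptions. The simulation also takes the primary gate as already passed. A mean statistic of 2.8 corresponds to about 80% marginal power, Φ(2.8−1.96) = Φ(0.84); a mean of 2.0 corresponds to about 52%, Φ(0.04). Each cell gives Hochberg, then the literal rule.

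| Mean, correlation | Mean rejections | P(at least one) | P(all four) |
|---|---|---|---|
| 2.8, 0.3 | 2.94 / 2.01 | 0.93 / 0.82 | 0.50 / 0 |
| 2.8, 0.5 | 2.92 / 2.03 | 0.89 / 0.79 | 0.55 / 0 |
| 2.8, 0.7 | 2.91 / 2.08 | 0.84 / 0.76 | 0.62 / 0 |
| 2.0, 0.3 | 1.54 / 0.86 | 0.68 / 0.44 | 0.15 / 0 |
| 2.0, 0.5 | 1.56 / 0.95 | 0.61 / 0.43 | 0.21 / 0 |
| 2.0, 0.7 | 1.60 / 1.06 | 0.54 / 0.42 | 0.29 / 0 |

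As a check, the gap in mean rejections should equal Hochberg's probability of at least one rejection, since exactly one is lost each time any endpoint qualifies. At mean 2.8 and correlation 0.5: 2.9185 − 2.0298 = 0.8887, which matches 0.89.

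The loss depends on correlation. At mean 2.0 the gap in P(at least one) halves, from 0.6769 − 0.4367 = 0.24 at correlation 0.3 to 0.5385 − 0.4218 = 0.12 at correlation 0.7. Only the zeros in the last column hold without assumptions.

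**The case against.** The best defence is that this is a slip in describing a procedure that is named clearly. SAP 5.2, SAP 6.3.3 and Protocol 9.4.5 all name Hochberg, and the ranking and critical values are correct. The faulty clause presents itself as an account of Hochberg, not as a variant. Read literally, it would leave a lone p = 0.001 unrejected although the same sentence counts it as below its critical value, so a missing *or equal to* is the natural explanation. A programmer using standard code would reject the qualifying endpoint.

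Most of this stands, and it rules out two stronger inferences:

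- A reader might infer that all four key secondaries can never be claimed in this trial. That would be so only if the clause overrode the method named in both documents, and nothing in them says that it does.
- A reader might infer that a standard Hochberg claim would contradict the plan. It would agree with Protocol 9.4.5 and with the method named in the SAP; it would disagree only with the written steps. The SAP is in conflict with itself.

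The objection does not remove the conflict. SAP 5.2 holds the only written steps in either document, and SAP 6.3.3 refers to them as the description of the procedure.

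**Conclusion.** Wrong as written, as a matter of wording. The choice of Hochberg and its critical values are sound. The decision sentence read literally excludes the qualifying test, which follows from the strict inequality alone and needs no assumption. Its size is one endpoint whenever any endpoint qualifies, more if p-values tie, and nothing if none qualifies.

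The direction is conservative, and the primary endpoint is untouched. What is at risk is a valid key secondary claim, or agreement after unblinding on which text governs. The simulated losses should not be read as this trial's chance of losing a claim: they rest on assumed power and correlation, they are conditional on a significant primary result, and they arise only if the clause is followed over the named method.

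**What to change.** Replace the decision sentence in SAP 5.2 with:

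> Find the largest rank j with p(j) <= 0.05/(k-j+1); reject the null hypothesis for that endpoint and for every endpoint with a smaller or equal p-value.

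This also settles the trivial case of a p-value exactly equal to its critical value. SAP 6.3.3 and Protocol 9.4.5 need no change, since they name the intended procedure and SAP 6.3.3 will then point to a correct description.

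The cost is one sentence, made before unblinding. It spends no additional alpha: the corrected rule is standard Hochberg, with simulated familywise error of 0.038 to 0.049 in the settings above.

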6 STATISTICAL ANALYSES

6.1 General

6.1.1 Programmed Output

A separate document contains the list of all TLFs, along with corresponding templates, attributes, and programming notes.

All output will be sorted and labeled according to the International Conference on Harmonisation (ICH) recommendations and formatted to the appropriate page size(s).

Medical history and AEs are coded using Medical Dictionary for Regulatory Activities (MedDRA) Version 24.

Concomitant medications are coded using World Health Organization Drug Dictionary (WHO-DD), released March 2021.

All statistical analyses will be performed using SAS statistical software (Version 9.4 or higher), unless otherwise noted.

6.1.1.1 Tables

Unless otherwise specified, the DB Phase and OLE Phase will be analyzed separately. For tables summarizing subjects who received at least one dose of DB or OLE study medication (Verdiperstat), summary statistics will be calculated from both phases combined for subjects randomized to Verdiperstat and from the OL Extension Phase for subjects randomized to placebo.

Treatment Group Presentation

Tables present results by treatment group (i.e., Verdiperstat and placebo) with the following exceptions:

- Results for the enrolled analysis set are presented only by overall, without treatment group.
- Results for study population parameters (see Section 6.2) and pre-treatment safety also include overall.

• OLE tabulations will include the sequence of the treatment, i.e., Verdiperstat/ Verdiperstat or Placebo/ Verdiperstat.

Time-to-event Tables

Time-to-event endpoints are summarized with KM tables displaying the following at each time interval:

- Number of subjects at risk, defined as those who did not have the event just prior to the start of the interval and who were not censored prior to the interval
- Number of subjects with events, defined as those who had the event for the first time during the interval
- Number of subjects censored, defined as those who did not have the event and whose censoring date/time (e.g., last contact date, last available measurement date/time) is in the interval
- Cumulative probability of having the event with lower and upper 95% CI limits, based on the KM product limit method.

Time-to-event distributions of endpoints are tabulated with the following descriptive statistics: number and percentage of subjects with events; number and percentage of subjects censored in or before the last time interval; number and percentage of subjects censored in the last time interval; time-to-event median, first quartile, and third quartile, with 95% CI. The 95% CI for the median is estimated using the method of Brookmeyer and Crowley.

6.1.1.2 By-Subject Listings

By-subject listings will display "Site-Subject ID (Age/Sex/Race)" stacked together in the same column using the following conventions:

- Age at informed consent will be displayed as an integer.
- Sex will be displayed abbreviated as "F" for female and "M" for male.
- Race will be displayed abbreviated as "A" for Asian", "B" for Black or African American, "I" for American Indian or Alaska Native, "M" for multiple, "N" for Native Hawaiian or Other Pacific Islander, and "W" for White.

A footnote will describe the abbreviations as applicable. Subjects who reported more than one race will be counted only once in the "Multiple" category. Missing age, sex, or race will be displayed as a single blank space.

Note that "(Age/Sex/Race)" will not be displayed in listings of randomization scheme and codes, batch numbers, or demographics.

6.1.1.3 Figures

Time-to-event endpoints are summarized graphically with KM plots that display cumulative percentage of having the event $(100 \times \text{cumulative probability}; \text{ see Section 6.1.1.1})$ on the y-axis versus time on the x-axis. Censored observations are denoted with symbols, and the number of subjects at risk at the start of each time interval are annotated below the x-axis.

6.1.2 Statistical Methods

Categorical variables will be tabulated with the count and percentage within each category (with a 'Missing' category if applicable). Continuous variables will be summarized with univariate statistics (e.g., n, mean, median, standard deviation (SD), minimum, and maximum). The median, minimum, and maximum values will be presented with the same precision as the data. The mean and percentiles will be presented with the precision of the data + 1 decimal place. The SD will be presented with the precision of the data + 2 decimal places.

Tabulations of the following endpoints present the number of unique subjects with an event: protocol deviations; non-study medications; AEs; and laboratory abnormalities. Thus, for these endpoints, multiple occurrences of the same event are counted only once per subject.

6.1.3 Handling of Missing Data

Unless otherwise noted, efficacy analyses will be based on observed data only. For the principal analysis of efficacy for primary, secondary and endpoints, no imputation will be performed on missing data following discontinuation from the study.

If the primary and secondary endpoints results are found to be statistically significant, then sensitivity analyses using multiple imputation (MI) will be conducted on the primary and key secondary endpoints using the copy increment from reference and jump to reference methods to assess the impact of the missing at random (MAR) assumption (see Section 6.3.2.3).

For efficacy analyses, partial or missing dates will not be imputed. The relative study days, where determined, will be calculated for full dates only.

If the start date of an AE is partially or completely missing, the date will be compared as far as possible with the date of the start of administration of study drug. The AE will be assumed to be treatment-emergent if it cannot be definitively shown that the AE did not occur or worsen during the treatment-emergent period (worst case approach).

The following general rules will be used:

• If the start day is missing but the start month and year are complete, an AE will only be excluded as being treatment-emergent if the start month/year is before the month/year of study drug administration or if the stop date is before study drug administration.

- If the start day and month are missing but the start year is complete, an AE will only be excluded as being treatment-emergent if start year is before the year of study drug administration or if the stop date is before study drug administration.
- If the start date is completely missing, an AE will be considered treatment-emergent unless the stop date is before study drug administration.

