4.4 End of Treatment

Patients will have a Week 48/Early Discontinuation visit when they either complete the study at Week 48 or discontinue from study medication early (prior to Week 48). The Week 48/Early Discontinuation assessments/procedures should be conducted as an in person visit at the study site. Every effort should be made to conduct the Week 48 visit and maintain a +/- 7 day window. However, due to the COVID-19 public health emergency, if absolutely necessary, in order to minimize potential risks to study participant safety and to comply with governmental and local institutional guidance (e.g., study site has a policy that an in person clinical research visit must be delayed), the Week 48 visit window may be expanded beyond the +/- 7 day window up to an additional 12 weeks (maximum treatment duration of 60 weeks). However, every attempt should be made to conduct the visit as close as possible to the date that the visit is due. Under these circumstances, the Investigator should discuss the specific circumstances of these cases with the sponsor medical monitor (or designee), who must

approve the request to extend the treatment duration, prior to any modification of the visit window.

If the Week 48 visit window is modified, participants should have safety assessments evaluated remotely (e.g., via phone) and safety labs conducted (at a local lab) at the time of the scheduled Week 48 visit.

For subjects who discontinue early, depending on the reason for early discontinuation (e.g., declining patient status), some procedures (for example, PK samples, PD samples, lumbar puncture), may not be conducted at this visit. Conduct of all procedures, if possible, is encouraged. If possible, the subjects who discontinue from study medication prior to Week 48 should be contacted by a follow up phone call at the approximate time of their Week 48 visit, to collect information on clinical status (including Time to Event measures of disease progression, and if applicable, AEs, SAES).

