4.5.2 Open-Label Extension Phase Procedures

When a site is open for recruitment to the OLE Phase, participants completing the double-blind treatment phase who choose to participate in the OLE phase and are eligible to continue, must consent to the OLE phase and directly enter the OLE phase starting at Week 48 visit of the double-blind treatment phase. The Week 48 visit will serve as the Baseline-Extension visit in the OLE phase for participants who move directly from the double-blind treatment phase to the OLE. Thereafter, participants will undergo visits at Week 2-Extension, Week 4-Extension, Week 8-Extension, Week 12-Extension, and then every 12 weeks of the OLE phase as outlined in [Table 2](#) (Schedule of Assessments & Events- Extension Phase).

A participant who has completed the double-blind treatment phase of the study prior to the OLE phase of the study being approved and open for recruitment at the study center where they are participating, can re-consent and start the OLE phase as long as the investigator determines that open-label treatment offers an acceptable risk-benefit profile for the participant. Once the study site is open for recruitment for the OLE, study participants who previously completed the double-blind phase of the study will have up to approximately 12 weeks (from the date of OLE opening at the site) to enroll and complete the OLE Baseline-Extension Visit, regardless of their date of double-blind phase completion.

For participants who have been off of the study drug for less than 4 weeks, the subject should attend an Abbreviated Drug Dispensation Visit at the investigative site, when medical and/or medication changes will be reviewed prior to dispensing open-label BHV-3241. In this case, for these participants, the Week 48 visit will also serve as the Baseline-Extension visit in the OLE Phase. Thereafter, participants will undergo visits at Week 2-Extension, Week 4-Extension, Week 8-Extension, Week 12-Extension, and then every 12 weeks of the Extension Phase as outlined in [Table 2](#) (Schedule of Assessments & Events- Extension Phase).

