6.4.1 Adverse Events

AEs will be coded using MedDRA and displayed in tables and listings by system organ class (SOC) and preferred term (PT), unless specified otherwise.

Analyses of AEs will be performed for those events that are considered treatment-emergent AEs (TEAEs), where treatment-emergent is defined as any AE that developed, worsened, or became serious on or after first dose of study drug and prior to 30 days after the last dose of study drug.

A TEAE overview without SOC and PT will be presented as the number and percentage of subjects with any of the following TEAEs: TEAE leading to death; serious TEAE; serious TEAE related to study drug; TEAE leading to study drug discontinuation; any TEAE; TEAE related to study drug; and severe AE.

In addition, TEAEs will be tabulated by SOC and PT for all treated subjects for the following endpoints for the DB and OLE phases, separately and combined:

- TEAEs
- TEAEs related to treatment (includes, possibly related and related)
- TEAEs by highest severity (mild, moderate, severe)

- TEAEs related to treatment by highest severity
- Treatment-emergent SAEs
- TEAEs leading to discontinuation of study treatment

In the above tabulations, each subject will contribute only once (i.e., the most related occurrence or the most severe occurrence) to each of the incidence rates in the descriptive analysis, regardless of the number of episodes.

The TEAEs summary by SOC and PT will also include the number of unique AE occurrences; unique occurrences mean that if a subject had an AE twice, both will be reported (i.e., the subject will contribute twice to the count of events).

All AEs occurring pre-treatment and during the entire study will be listed. Additional listings will be provided including deaths, SAEs, AEs leading to discontinuation of study drug, and events of special interest (see Section 6.4.2).

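### The partial-date bullets in SAP 6.1.3 set no upper limit, so a partially dated adverse event known to have begun after the treatment-emergent period is still counted, contrary to SAP 6.4.1 and the section's own lead-in

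*SAP*

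**What the plan says.** SAP 6.1.3 (Handling of Missing Data) opens its adverse-event text by saying that, for a partial or missing start date, "the date will be compared as far as possible with the date of the start of administration of study drug". It then states a principle: the event is assumed treatment-emergent "if it cannot be definitively shown that the AE did not occur or worsen during the treatment-emergent period (worst case approach".

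Three bullets put this into operation.

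- Day missing, month and year known: "an AE will only be excluded as being treatment-emergent if the start month/year is before the month/year of study drug administration"; an event that had already ended when dosing began is dropped too.
- Day and month missing, year known: "an AE will only be excluded as being treatment-emergent if start year is before the year of study drug administration"; again, an event that had already ended when dosing began is dropped too.
- Start wholly missing: "If the start date is completely missing, an AE will be considered treatment-emergent unless the stop date is before study drug administration".

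SAP 6.4.1 (Adverse Events) defines a treatment-emergent event as one that arose, got worse or turned serious "on or after first dose of study drug and prior to 30 days after the last dose of study drug". It tabulates these events for the double-blind and extension phases separately and combined.

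SAP 7.1 (Analysis Periods) gives separate on-treatment periods. For safety in subjects who enter the extension, the double-blind period closes at the first day of open-label drug or 30 days after the last double-blind dose, whichever comes first. The extension period starts with the first open-label dose.

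**The concern.** The word only in the first two bullets makes the list of exclusions exhaustive, and every exclusion looks backwards to the start of dosing. The last dose is never mentioned. A program written from the bullets would therefore classify an event by how completely its date was recorded: outside the period if the day is known, inside it if the day is missing.

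Events after the period can reach the database. Protocol 4.4 says subjects who stop study medication early "should be contacted by a follow up phone call at the approximate time of their Week 48 visit", and that call collects adverse events where applicable. Protocol 8.2.1 says when collection of non-serious events begins and names no end. Protocol 4.5.2 lets subjects who finished the double-blind phase before the extension opened at their site enter it "regardless of their date of double-blind phase completion", so events from an off-drug gap may be reported at the extension baseline visit. Events recalled after a long interval are plausible candidates for partial dates.

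The phases raise a second problem. The bullets refer to study drug administration without saying which phase is meant. With no upper limit, an event that began on open-label drug is not excluded from the double-blind tables. At stake is the accuracy of the treatment-emergent tables, some of which serve the safety part of the primary objective. No efficacy analysis depends on this rule.

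**Working it through.** The documents state no figure that depends on this rule, so there is none to reproduce. The check applies two readings to the same partial dates:

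- Reading A: the bullets exactly as written.
- Reading B: the lead-in principle with the SAP 6.4.1 period. An event is excluded if its latest possible start is before the first dose, or its earliest possible start is after the last treatment-emergent day.

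The calendar dates are assumptions for illustration.

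**Subject who stops early.** First dose 15 Jan 2020, last dose 15 Mar 2020. The period ends before last dose + 30 days, so the last day inside it is 15 Mar + 29 days = 13 Apr 2020.

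| Recorded start | Reading A | Reading B |
|---|---|---|
| Dec 2019 | excluded | excluded |
| Apr 2020 | counted | counted |
| 2020 (month unknown) | counted | counted |
| wholly unknown | counted | counted |
| May 2020 | counted | excluded |
| Sep 2020 | counted | excluded |
| 2021 (month unknown) | counted | excluded |

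The readings differ only in the last three rows, where even the earliest possible start is past 13 Apr 2020. A start after the period also rules out worsening within it. A fully dated start of 10 Sep 2020 is 179 days after the last dose and is not treatment-emergent under SAP 6.4.1. Recorded as Sep 2020, the same event is counted under Reading A.

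**Subject who enters the extension directly.** First blinded dose 15 Jan 2020; last blinded dose and first open-label dose both 16 Dec 2020 (Day 337); randomized to placebo.

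- Start recorded as Jun 2021. The month is not before Jan 2020, so the bullets do not exclude the event from the double-blind placebo column. SAP 7.1 closed that period on 16 Dec 2020.
- Start recorded as Jan 2021. A limit of last blinded dose + 30 days would still count it, because the last day inside is 16 Dec + 29 days = 14 Jan 2021. The earlier-of rule in SAP 7.1 would not. The end limit for the double-blind tables therefore has to be the one in SAP 7.1.
- Start recorded as Jun 2020. If the anchor is the first blinded dose, the bullets do not exclude this placebo event from the extension or combined verdiperstat tables. If the anchor is the first open-label dose, they do. SAP 6.1.3 does not say which applies.

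**Reach of the Week 48 call.** The call is at about Day 337. For a stop on Day s, the last day inside the period is s + 29 and the days outside it number 337 − (s + 29).

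| Stop day | Last day inside | Days outside / days since stop |
|---|---|---|
| 85 | 114 | 223 / 252 = 88% |
| 169 | 198 | 139 / 168 = 83% |
| 253 | 282 | 55 / 84 = 65% |

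These are shares of calendar days, not of events. If the planned drop-out of about 20% (SAP 5.1) is taken as the share stopping early, about 0.20 × 325 = 65 subjects could be reached by this route. The open-label route is not bounded by that number.

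**The case against.** The best defence is the lead-in sentence. It ties the test to the treatment-emergent period, and SAP 6.4.1 gives that period an end. A reader might infer that the SAP has no end limit at all for partially dated events, and that goes too far: the limit is in the principle and missing from the bullets. The defence does not remove the fault. The bullets state the exhaustive exclusions and are what a programmer would code, and the SAP does not say which text prevails.

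A reader might also infer that every late event with a missing day or month is misclassified. It is not. Where the known month or year overlaps the period, counting the event is the intended worst-case result and should stay.

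On phases, SAP 7.1 defines the periods, SAP 6.1.1.1 says combined tables use only extension data for placebo-randomized subjects, and SAP 6.4 names the populations. That largely answers which doses should apply. What stands is that SAP 6.1.3 does not point to any of it.

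On size, it is tempting to multiply the planned drop-out by a guessed share of late, partly dated reports and quote percentage points, or a false difference between arms. The documents give no such share and no drop-out by arm. A subject with another treatment-emergent event adds nothing to the overall rate, because each subject is counted once. The call itself is made if possible.

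The link to the primary safety endpoint is also narrower than it looks. An event that begins months after the last dose cannot have caused stopping, and Protocol 8.1.4 asks for serious events beyond 30 days only if believed related.

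**Conclusion.** The point holds as an internal contradiction. For a partial start date whose earliest possible day is already past the treatment-emergent period, the first two bullets of SAP 6.1.3 count the event, while SAP 6.4.1 and the lead-in of the same section do not. The bullets are also not linked to the phase periods of SAP 7.1. This is more than missing detail, because following the rule as written gives a wrong classification.

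The number of affected events is unknown and probably small: routine collection of serious events ends 30 days after dosing, and late reports from early stoppers depend mainly on one call. Post-treatment events cause over-counting. Open-label events can be added to the double-blind count of either arm, including placebo, so the error is not conservative in every table. The conclusion rests on the bullets being coded as written; a programmer who let the lead-in and SAP 7.1 govern would avoid it.

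**What to change.** Add to bullets 1 and 2 of SAP 6.1.3 that an event is also excluded as treatment-emergent for a phase if the earliest date consistent with its partial start date falls after the end of that phase's treatment-emergent period.

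State that the limits are those of SAP 6.4.1, applied per phase as in SAP 7.1:

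- the double-blind period ends at the first open-label dose or 30 days after the last double-blind dose, whichever is earlier;
- for placebo-randomized subjects in the extension and combined verdiperstat tables, the period starts at the first open-label dose.

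Add no end limit to bullet 3. A wholly missing start date has no earliest possible date to compare, and the worst-case rule should go on applying there.

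The cost is a few sentences in the SAP and one condition in the adverse-event program, using phase-specific first and last dose dates that SAP 6.2.6.1 already needs for exposure. No new data are required. It should be settled before unblinding.
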